9.0 Data Analysis

The data analysis will be performed on de-identified data by the primary investigator, [name], who has extensive experience in the statistical analysis of PCa outcomes and biomarkers. [name], a co-investigator who is a world expert in PCa biomarker study design and analysis, will provide analytical support and oversight. Statistical methods are outlined in section 12 below.

10.0 Quality Control and Quality Assurance

The quality of the MRI images will be assessed qualitatively by the scanner technician in the Advanced Imaging Center at the time of data acquisition. In addition, the source and processed images will be assessed for acceptable quality by the study radiologist ([name]). It is possible that a patient would need to undergo a repeat MRI if the data are not adequate for assessment for PCa. All pathologic analysis is subject to the UIC Department of Pathology clinical quality assurance procedures as is the current clinical SOC.

11.0 Data and Safety Monitoring

Privacy of protected health information will be maintained by minimizing identifiable patient data and maintaining this information in a secure database for use only by study investigators. All identifiers needed for the research will be kept in the secure REDCap server. Only de-identified data will be retrieved from the server in order to perform data analyses

12.0 Statistical Considerations

As this is a single arm pilot study, no power analysis is necessary. Based on the PRECISION study, we expect a high grade PCa detection rate of approximately 30% or in 17/50 subjects (10). The primary outcome will be the comparison of the rate of high grade PCa detection based on the 2 possible MRI outcomes: men undergoing standard

12 core TRUS biopsy (detection protocol MRI negative) versus men undergoing MRI targeted biopsy (detection protocol MRI positive for lesions). This will be analysed for statistical difference using the chi-square test. Each MRI quantitative parameter will be evaluated on a per lesion basis as a predictor of high grade PCa using ROC logistic regression and will be reported as AUC with 95% confidence intervals (CI). The Youden's Index and 90% fixed sensitivity thresholds of each quantitative parameter will be reported. Combinations of MRI quantitative and clinical parameters will be combined into multinomial logistic regression models for which AUC with 95% CI will be reported. The AUC of the multi-parametric models will be compared iteratively for statistical differences using the likelihood ratio test.

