1.0 Project Summary/Abstract

Currently men with elevated prostate specific antigen (PSA) or abnormal digital rectal examination (DRE) undergo systematic sampling of the prostate with transrectal ultrasound (TRUS)-guided needle biopsies. PSA and DRE have low specificity for prostate cancer (PCa), and TRUS biopsies have an approximately 30% false negative rate. Whether a quantitative detection specific magnetic resonance imaging (MRI) protocol improves PCa detection in biopsy naïve men is not adequately studied.

This pilot study aims to test a novel detection specific MRI protocol which uses image collection and post-processing to assist the radiologist find areas of the prostate with increased suspicion for clinically significant cancer. Men with an MRI negative for cancer will undergo standard of care TRUS biopsies, and men with suspicious MRI lesions (as defined by our preliminary data) will undergo biopsies of these lesions in addition to systematic TRUS biopsies. We will compare the yield of significant PCa between systematic sampling and MRI determined areas of the prostate.

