3.0 Objectives/Aims

This study aims to determine whether a detection specific MRI protocol with quantitative image analysis can improve high grade PCa detection in men with clinical suspicion and no prior biopsy.

Aim 1: Design a PCa detection specific MRI protocol which will facilitate quantitative image analysis and reduce study time by ~50%

Current prostate mpMRI protocols include image sequences and fields of view outside of the prostate gland and its immediate surrounding that are not useful for PCa detection. We will create a detection specific MRI protocol featuring: smaller fields of view zoomed to the prostate, T2 weighted imaging at multiple echo times, chemical exchange saturation transfer imaging (CEST), and DWI at higher b values (up to 4000) that will allow for quantitative prediction of high grade PCa. The exact imaging acquisition parameters can be found in Appendix 3. We expect this MRI protocol to

reduce study (acquisition) time from approximately 45 minutes to 27 minutes, which will potentially lower cost and improve tolerance of the procedure. Significantly, we will omit DCE which will reduce the imaging time, and the risks associated with intravenous contrast including systemic fibrosis, and patient discomfort.

Aim 2: Determine the accuracy of the novel MRI protocol for detection of high grade PCa

50 men with clinical suspicion of PCa (elevated PSA and/or abnormal DRE) will be enrolled into a prospective protocol and will undergo detection protocol MRI described in Aim 1. Quantitative image analyses will be performed to generate SEM maps of DWI. Areas of suspicion for high grade PCa (GS ≥ 7) will be targeted for biopsy. Men with MRI with no areas of suspicion for high grade PCa will undergo standard of care 12 core TRUS biopsy. The primary endpoint will be the rate of detection of high grade PCa on the per patient and per biopsy core basis. Men with biopsy pathology negative for PCa will undergo standard of care (SOC) continued monitoring.

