5.0 Study Design and Procedures

This will be a single arm prospective clinical trial. Men with clinical suspicion for PCa but no prior prostate biopsy will be enrolled from the UI Health Urology clinics. All eligible men will be screened and enrolled by the clinical research coordinator. Enrolled men will undergo detection protocol MRI at the UIC Advanced Imaging Center (AIC) prior to diagnostic biopsy. The image acquisition parameters are listed in the Appendix 3. The MRI will be processed by the study team and evaluated for areas suspicious for high grade PCa by a board certified clinical radiologist ([name]). Subjects with MRI with no suspicious areas for high grade PCa will undergo SOC 12 core TRUS biopsy. Subjects with MRI suspicious for high grade PCa will have 2-4 biopsies guided toward each suspicious lesion using MRI/TRUS fusion biopsies (maximum of 12 cores). All biopsies will undergo SOC histologic processing and interpretation in pathology. Biopsy results will be communicated to the patients by the Urologist performing the biopsy and all additional management will be SOC. This visit will signify the end of the study. See the study schema in Figure 4.

[figure not shown]

Figure 4: Study schema

The primary outcome will be the rate of detection of high grade PCa on a per-patient and per biopsy core basis. The detection rate will be compared between patients with and without evidence of high grade PCa (GS ≥ 7) based on the detection protocol MRI. Secondarily we will analyze the accuracy of the individual MRI parameters including: T2 imaging, ADC, the SEM parameters (DDC and α), the FROC parameters (μ , Δ , β), the Kurtosis model parameters (D, K), and PI-RADS score.

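### The primary chi-square compares two MRI-directed biopsy pathways and cannot answer the improved-detection objective; section 1.0 conflicts with later sections on systematic cores in MRI-positive men

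*Combined protocol and SAP*

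**What the plan says.** **Objective.** Section 3.0 sets out to "determine whether a detection specific MRI protocol with quantitative image analysis can improve high grade PCa detection". Its second aim reads: "Aim 2: Determine the accuracy of the novel MRI protocol for detection of high grade PCa".

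**Primary outcome and test.** Section 5.0 (Study Design and Procedures) states: "The primary outcome will be the rate of detection of high grade PCa on a per-patient and per biopsy core basis". Section 12.0 compares men having standard "12 core TRUS biopsy (detection protocol MRI negative) versus men undergoing MRI targeted biopsy (detection protocol MRI positive for lesions", using a chi-square test.

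**Biopsy in MRI-negative men.** Section 3.0: "Men with MRI with no areas of suspicion for high grade PCa will undergo standard of care 12 core TRUS biopsy". Sections 1.0, 5.0 and 12.0 agree.

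**Biopsy in MRI-positive men.** The sections differ.
- Section 1.0 says that men with suspicious lesions "will undergo biopsies of these lesions in addition to systematic TRUS biopsies", and adds: "We will compare the yield of significant PCa between systematic sampling and MRI determined areas of the prostate".
- Section 3.0 says only that suspicious areas will be targeted.
- Section 5.0 (Study Design and Procedures) says that these men "will have 2-4 biopsies guided toward each suspicious lesion using MRI/TRUS fusion biopsies (maximum of 12 cores". It does not mention systematic cores.
- Section 8.0 records biopsy type as standard or targeted, and a maximum Gleason score that is not tied to core type.

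**Other analyses.** Section 12.0 also plans per-lesion AUCs for each quantitative parameter. It plans no within-man comparison of core types and no patient-level sensitivity or specificity.

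**The concern.** In the primary comparison, MRI result and biopsy method change together, so a difference in detection mixes two things: how well the MRI sorts men, and how well each kind of biopsy finds the cancer that is there. The endpoint sits under an accuracy aim and an improvement objective, but the test supplies neither quantity.

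The analysis that could bear on improvement is the one promised in section 1.0. It needs both core types in the same men. If MRI-positive men have targeted cores only, it cannot be done. If they have both, section 12.0 has no analysis of it. Either way, following the plan leaves that comparison undone. If operators follow different sections, the missing core type cannot be recovered after the biopsy.

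**Working it through.** **1. The plan's own figure.** Section 12.0 expects about 30%, written as 17/50. 0.30 × 50 = 15, and 17/50 = 34%. The mismatch is small and does not affect this point. The plan gives no power, alpha or group split to reproduce.

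**2. What the test compares.** Let se_T and se_S be the sensitivity of targeted and systematic cores for high grade disease, and assume no false positive pathology.
- Observed rate, MRI-positive = PPV × se_T
- Observed rate, MRI-negative = (1 − NPV) × se_S
- Difference = PPV × se_T − (1 − NPV) × se_S

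**3. Contribution of the biopsy method alone.** If the MRI is uninformative, both groups have the same prevalence π and the difference is π(se_T − se_S). Inputs:
- Split 36/14: section 2.0 reports 28% MRI-negative in the cited European trial, and 0.28 × 50 = 14 (assumed to carry over).
- se_S = 0.70: from the roughly 30% TRUS false negative rate in section 1.0, which is not specific to high grade disease.
- π = 48.6% (0.34/0.70), or 34% as an alternative (both assumed).
- Uncorrected chi-square, two-sided 0.05 (assumed), both binomials fully enumerated.

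| π | se_T | MRI-positive rate | MRI-negative rate | Rejection |
|---|---|---|---|---|
| 48.6% | 0.70 | 34.0% | 34.0% | 4.9% |
| 48.6% | 0.95 | 46.2% | 34.0% | 12.4% |
| 34% | 0.70 | 23.8% | 23.8% | 4.6% |
| 34% | 0.95 | 32.3% | 23.8% | 8.0% |

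**4. Improved detection.** Let a and b be the cancers found in MRI-positive and MRI-negative men, and s the number that systematic cores would find in the same MRI-positive men.
- Pathway yield = (a + b)/50
- Systematic yield in all men = (s + b)/50
- Gain = (a − s)/50

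The chi-square uses a and b but not s. Take 15/36 against 2/14 as an example (17/50 overall, p = 0.066). With s = 10, 13 or 15 the gain is +10, +4 or 0 percentage points, and the p-value is the same each time.

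**5. Patient-level accuracy.** For the same table:
- MRI sensitivity = (a/se_T) / (a/se_T + b/se_S)
- MRI specificity = (14 − b/se_S) / [(14 − b/se_S) + (36 − a/se_T)]

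With se_T = 1.0 and se_S = 0.5: 15/(15 + 4) = 0.79 and 10/(10 + 21) = 0.32. With both at 0.70: 21.4/(21.4 + 2.9) = 0.88 and 11.1/(11.1 + 14.6) = 0.43. One observed table fits both pairs.

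**6. What the repaired analyses could deliver.**
- *Paired comparison*, assuming se_T = 0.90, se_S = 0.70 and independent misses. Expected discordant men are n × PPV × se_T × (1 − se_S) and n × PPV × (1 − se_T) × se_S.
  - n = 36, PPV 0.42: 4.1 and 1.1; exact McNemar power about 10%.
  - n = 34, PPV 0.576 (prevalence 43%, MRI sensitivity 0.90, specificity 0.50: 0.387/0.672): 5.3 and 1.4; power about 18%.
- *Apparent rates*, exact 95% intervals: 1/14 gives 0.2% to 33.9%; 14/36 gives 23.1% to 56.5%.

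**The case against.** **The test is valid for what it is.** Section 5.0 (Study Design and Procedures) openly defines the contrast as detection in men with and without MRI evidence of high grade disease. That is a question of association, and the study is a pilot. This stands: the chi-square is not invalid. No section says that the test will prove improvement. The point is that nothing else in section 12.0 answers the section 3.0 objective either.

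**Accuracy is addressed elsewhere.** The per-lesion AUCs and thresholds do bear on Aim 2 and do not rest on the primary comparison. But they are confined to men with lesions, so they cannot give patient-level sensitivity or specificity.

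**A significant result may be correct.** A reader might infer that significance without improvement is a false positive. It need not be. With prevalence 43%, MRI sensitivity 0.90 and specificity 0.50, a 34/16 split, and both biopsy methods 70% sensitive, the pathway and systematic biopsy of all men each find 15.05 cancers on average, and the test rejects 67% of the time. That 67% is power to detect a real association, not error. It shows only that significance and improvement are different questions.

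**The contradiction may be narrower than it looks.** Section 1.0 is the outlier. A reader might infer that MRI-positive men are denied systematic cores. The text does not go that far: systematic cores are omitted, not excluded, and the 12-core maximum may cap targeted cores only. The Figure 4 schema and the Appendix 4 data flow, which could settle it, are not visible in the text reviewed. The written sections still need to agree.

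**Replacing the test would not help.** A reader might conclude that the primary test should instead compare the MRI groups on systematic cores alone. On the assumed inputs that comparison lies further from the true difference and has less power, so it is not recommended.

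**Conclusion.** The point holds in two parts.

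1. Section 1.0 conflicts with sections 3.0, 5.0 (Study Design and Procedures) and 12.0, and with the biopsy-type field in section 8.0, on whether MRI-positive men have systematic cores. The yield comparison promised in section 1.0 is either impossible or unanalysed. This part rests on the text alone.
2. As sections 5.0 and 12.0 read, the primary chi-square compares apparent PPV with apparent 1-NPV, measured by different biopsy methods. It tests association, with some contamination by method: rejection of about 8% to 12% in place of about 5% under an uninformative MRI and targeted sensitivity 0.95. That size depends on assumed prevalence, split and biopsy sensitivities, and is modest. That the test cannot show improved detection, or give patient-level sensitivity or specificity, does not depend on those inputs.

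This must be fixed, because the plan followed exactly leaves its stated objective unanswered. The documents do not support calling the chi-square invalid, or treating every significant result as an artefact of biopsy method.

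**What to change.** The sponsor must reconcile section 1.0 with sections 3.0, 5.0 (Study Design and Procedures), 8.0 and 12.0 on the cores taken in MRI-positive men. Which biopsy scheme is right is not judged here. The analysis then follows from the answer.

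- **If both core types are taken in MRI-positive men:** record Gleason score by core type. Add to section 12.0 the paired targeted-versus-systematic difference in high grade detection within these men, with a confidence interval. Present it as an estimate only, since McNemar power is about 10% to 18% under the assumed inputs.
- **If targeted cores only:** delete the yield comparison in section 1.0. Label the primary test a comparison of MRI-directed pathways. Report apparent PPV and apparent 1-NPV with exact confidence intervals, stated as measured by different biopsy methods. Make no claim of improved detection from it.

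Cost: a protocol amendment, a rewritten analysis paragraph and, in the first case, a clarified Gleason field. This review imposes no extra patients or procedures. The price is a narrower claim in the second case and imprecise estimates in both.

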8.0 Data Collection and Management Procedures

To meet the study goals, clinical, imaging, and pathologic data will be collected prospectively. The co-investigators and other key personnel will have access to the identified data while the subject is on study. A REDCap database will be used to record all of the baseline and clinical data for each subject including: age (continuous in years), self reported race (white, black, Hispanic, other), family history of prostate cancer (positive or negative), serum PSA (continuous, in ng/mL), International Prostate Symptoms Score (IPSS: continuous), Sexual Health Inventory for Men score (SHIM: continuous). All source MRI images from the scanner as well as post-processed images will be collected in Digital Imaging and Communications in Medicine (DICOM) format. Image data will be stored on a password protected server and physically transported from the scanner to the post-processing workstation and to the radiologist workstation using an encrypted flash drive. Data from interpretation of the MRI images to be stored in REDCap will include: PI-RADS score (ordinal), number of lesions (ordinal), and the lesion mean, median, minimum and maximum for each quantitative MRI parameter if applicable. In addition, if applicable each lesion will be outlined on the T2 weighted image series by the radiologist for use at the time of biopsy. At the time of biopsy the prostate volume (continuous, cubic centimeters), type of biopsy (standard or targeted), and number of biopsy cores obtained (ordinal) will be entered in REDCap. Pathology data to be collected and stored in REDCap includes: presence of any carcinoma (Boolean), number of biopsy cores involved with carcinoma (ordinal), location of positive biopsy cores (ordinal lesion number), and maximum GS of biopsies (categorical:

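### The per-lesion ROC leaves out men with a negative MRI, so its AUCs and 90% sensitivity thresholds hold only among lesions already called suspicious and do not measure detection accuracy in biopsy-naive men

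*Combined protocol and SAP*

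**What the plan says.** All references are to the combined protocol and SAP.

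- **Unit of analysis (section 12.0):** "Each MRI quantitative parameter will be evaluated on a per lesion basis as a predictor of high grade PCa using ROC logistic regression". AUCs with 95% confidence intervals are planned, and "The Youden's Index and 90% fixed sensitivity thresholds of each quantitative parameter will be reported".
- **Recorded parameter values (section 8.0):** "the lesion mean, median, minimum and maximum for each quantitative MRI parameter if applicable". No regional or whole-gland value is listed.
- **Recorded pathology location (section 8.0):** "location of positive biopsy cores (ordinal lesion number"). A standard core from a man without a lesion has no such number.
- **MRI-negative men (section 5.0, Study Design and Procedures):** "Subjects with MRI with no suspicious areas for high grade PCa will undergo SOC 12 core TRUS biopsy".
- **MRI-positive men:** the same section says they "will have 2-4 biopsies guided toward each suspicious lesion using MRI/TRUS fusion biopsies". Section 1.0 says instead that "men with suspicious MRI lesions (as defined by our preliminary data) will undergo biopsies of these lesions in addition to systematic TRUS biopsies".
- **How lesions are chosen (section 3.0, Aim 2):** "Quantitative image analyses will be performed to generate SEM maps of DWI. Areas of suspicion for high grade PCa (GS ≥ 7) will be targeted". Section 5.0 adds that the study team processes the MRI before the radiologist evaluates it.

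Section 5.0 makes parameter accuracy a secondary analysis. The primary outcome is the high grade detection rate, compared between MRI-negative and MRI-positive men.

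**The concern.** Aim 2 asks how accurate the protocol is for detecting high grade cancer in men with clinical suspicion and no prior biopsy. Sensitivity for that purpose needs every high grade cancer found in the denominator. The per-lesion ROC can count only cancers in lesions that were called suspicious. Cancers found by the 12-core biopsy in MRI-negative men drop out, and those are the ones the MRI missed.

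The lesions that do enter may also have been chosen partly on the parameters being evaluated. Such selection narrows the range of those parameters. It can lower their AUCs relative to parameters that played no part in the choice.

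The 90% sensitivity threshold is the result most likely to be carried into a later study. Section 7.0 looks ahead to avoiding biopsy after a negative MRI. A threshold read as finding 90% of high grade cancers, when it finds 90% of those already flagged, would mislead that step.

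**Working it through.** **Step 1: who can enter.** No sentence excludes MRI-negative men; the exclusion follows from the unit of analysis and the data fields. A per-lesion ROC needs a parameter value and a biopsy outcome for each unit. An MRI-negative man has neither under section 8.0. Section 12.0 plans no regional or per-man ROC for the parameters, no correction for selection, and no limit on interpretation. If the 28% negative share that section 2.0 quotes from the PRECISION trial applied here (an assumption), 0.28 × 50 = 14 men would contribute nothing and 36 would remain.

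**Step 2: expected cancers.** Section 12.0 gives about 30%, or 17 of 50. The two differ: 0.30 × 50 = 15, and 17/50 = 34%. Both counts are carried forward.

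**Step 3: what a nominal 90% threshold detects.** Let N be the high grade cancers found and x the number in MRI-negative men. Assume one index lesion per man, and count a man without a lesion as test negative. Then

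sensitivity among all found = 0.90 × (N − x) / N

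| x | N = 15 | N = 17 |
|---|---|---|
| 0 | 90% | 90% |
| 1 | 0.90 × 14/15 = 84% | 0.90 × 16/17 = 85% |
| 2 | 0.90 × 13/15 = 78% | 0.90 × 15/17 = 79% |
| 3 | 0.90 × 12/15 = 72% | 0.90 × 14/17 = 74% |

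The documents do not give x. The nominal figure is right only if x = 0.

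**Step 4: effect of selection on the AUC (illustration).** The model was an equal-variance binormal marker with 1,000,000 units, one per man, and prevalence of 30% or 34%. The lowest 28% on a selection score were removed. The score separated cancers as well as the parameter did, and its within-class correlation with the parameter ran from 0.3 to 1.0.

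| AUC in all men | AUC among selected | Cancers in excluded group | Sensitivity of the 90% threshold among all cancers |
|---|---|---|---|
| 0.70 | 0.65–0.68 | about 13% | 78–79% |
| 0.80 | 0.74–0.78 | about 7% | 84% |
| 0.85 | 0.79–0.83 | about 4% | 86–87% |

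The fall in AUC grows with the correlation. In a separate run, a parameter with AUC 0.80 that was conditionally independent of the selection score stayed at 0.80. Two equally accurate parameters could therefore be reported with different AUCs.

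**Step 5: size against precision.** With 36 units, 15 to 17 of them positive, and AUC 0.80, the Hanley-McNeil standard error is 0.079 to 0.076. The 95% half-width is 1.96 × 0.079 = 0.15 (or 1.96 × 0.076 = 0.15). The modelled AUC shift of 0.02 to 0.06 is well inside that.

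**The case against.** The strongest reply is that the lesion-only ROC answers a question the study does ask. Section 2.0 hypothesises that quantitative tools can help radiologists characterise indeterminate studies as an adjunct to PI-RADS, and the preliminary work graded targeted lesions. For that purpose, conditioning on a suspicious lesion is correct. This stands, and it is why the analysis should be kept and labelled. It does not cover the detection use, which section 2.0 also states when it proposes quantitative DWI to determine which regions are suspicious.

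The analysis is also secondary, in a pilot of 50. That stands and limits the weight of the point.

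A reader might infer more than the documents support:

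- **That Aim 2 as a whole, or its primary comparison, fails.** It does not on this ground. MRI-negative men and their 12-core results are in the chi-square comparison. PI-RADS is recorded separately from the lesion summaries and is not clearly confined to lesions.
- **That a true AUC of 0.80 would fall to about 0.67–0.72.** That needs the evaluated parameter alone to select the top 30% to 50% of regions. No such rule is written: a radiologist judges processed images, and section 1.0 refers only to preliminary data.
- **That the ranking of parameters is shown to be biased.** It may be, but the documents do not say how strongly each parameter drives selection.
- **That a ROC pooling all men should replace the lesion ROC as the main one.** Pooling has its own bias. Under section 5.0, MRI-negative men are verified by 12 cores and MRI-positive men by targeted cores, and section 1.0 puts the TRUS false negative rate at about 30%.

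**Conclusion.** The concern holds for the AUCs, Youden thresholds and 90% sensitivity thresholds of the quantitative parameters. As planned, they are conditional on a suspicious lesion and do not measure detection accuracy in biopsy-naive men.

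The missing denominator is the firm part. One to three high grade cancers in MRI-negative men bring a nominal 90% down to between 85% and 72% of the high grade cancers found, under the index-lesion and test-negative assumptions above. Cancers that TRUS itself misses are not counted in these figures.

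The lowering of DWI/SEM AUCs is plausible but not sized by the documents. The illustration of 0.80 becoming 0.74–0.78 rests on the borrowed 28% share, the binormal model and a within-class correlation of 0.3 to 1.

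**What to change.** 1. **Section 12.0:** label the lesion-based AUCs, Youden thresholds and 90% sensitivity thresholds as applying *among lesions called suspicious*.
2. **Sections 8.0 and 12.0:** for each parameter, extract one most-suspicious value per man from the maps already generated. Prespecify the rule and apply it identically whether or not a lesion was called. Add a per-man ROC of all biopsied men against any GS ≥ 7 on biopsy. Take from it any 90% sensitivity threshold offered for detection.
3. **Section 8.0:** record the template site of each standard core, so that a regional analysis is possible as exploratory work. This has to be captured at biopsy.
4. **Sections 1.0, 3.0 and 5.0 (Study Design and Procedures):** reconcile whether MRI-positive men have systematic cores as well as targeted ones. The answer decides what a regional analysis can use in those men.

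No extra scan or biopsy is needed. The cost is one data field and modest post-processing. Any regional matching must fit with section 13.2, which de-identifies the data about a week after biopsy. The report should state two downsides. Sensitivities will look less favourable. The reference standard will also differ by MRI result, so cancers missed by TRUS still count as negative.

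### Section 12.0 compares AUCs with the likelihood ratio test, which does not test them, and plans no nesting limit, no allowance for several lesions per man and no internal validation

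*Combined protocol and SAP*

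**What the plan says.** Section 12.0 sets out the secondary accuracy analyses in four steps.

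- Single parameters: "Each MRI quantitative parameter will be evaluated on a per lesion basis as a predictor of high grade PCa", reported as AUC with a 95% confidence interval.
- Cut-offs: "The Youden's Index and 90% fixed sensitivity thresholds of each quantitative parameter will be reported".
- Combined models: "Combinations of MRI quantitative and clinical parameters will be combined into multinomial logistic regression models for which AUC with 95% CI will be reported".
- Comparison of those models: "The AUC of the multi-parametric models will be compared iteratively for statistical differences using the likelihood ratio test".

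The parameters are listed under Study Design and Procedures: "Secondarily we will analyze the accuracy of the individual MRI parameters including: T2 imaging, ADC, the SEM parameters" (DDC and α), then three FROC parameters (μ, Δ, β), and "the Kurtosis model parameters (D, K), and PI-RADS score". Section 8.0 stores "the lesion mean, median, minimum and maximum for each quantitative MRI parameter if applicable". A man may contribute more than one lesion, because the biopsy procedure takes "2-4 biopsies guided toward each suspicious lesion using MRI/TRUS fusion biopsies" and Section 8.0 records the number of lesions.

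The documents name no paired test of AUCs, no method for within-man correlation, and no cross-validation, bootstrap or split sample. They do not give the terms or size of any combined model, or the expected number of lesions.

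**The concern.** The hypothesis and the test do not match. The likelihood ratio test has as its null that the added coefficients in the larger of two nested models are zero. Equality of two AUCs is a different hypothesis. A p value presented as showing that one model has the higher AUC would not answer that question.

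Three gaps surround the mismatch.

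1. Nothing limits the comparison to nested models, although the parameter list contains rival diffusion sets, none of which contains another.
2. Lesions in one man share that man's biology and scan, and recorded clinical variables such as age, PSA and family history are identical for all his lesions. Treating lesions as independent misstates the uncertainty.
3. Combined-model AUCs and Youden cut-offs would be judged on the data that produced them, which flatters both. A confidence interval around an apparent AUC does not remove that bias.

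Quantitative accuracy is the study's rationale (Sections 2.0 and 3.0), and these AUCs and cut-offs are what a later study would carry forward.

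**Working it through.** **The plan's own figure.** Section 12.0 expects high grade cancer in about 30%, or 17 of 50 men. 0.30 × 50 = 15, and 17/50 = 34%, so both 15 and 17 are carried. These are men across both MRI groups. Using 15–17 as counts of high grade lesions is an assumption.

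**Assumed inputs.** Section 2.0 cites 28% negative MRI in the European trial. If that carried over, 50 × (1 − 0.28) = 36 men would have a lesion. Lesion counts of 36 to 72 were simulated, about a third high grade in most settings. The outcome is taken as binary (high grade or not), although the plan names multinomial regression. Within-man and between-marker correlations are assumptions.

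**1. What the test does.** LR = 2 × (log-likelihood of larger model − log-likelihood of smaller), referred to chi-square with degrees of freedom equal to the number of added terms. AUC does not enter it. In a nested simulation with 50 units, 1,129 tests were significant. The AUC gain was below 0.03 in 111 of them (111/1,129 = 9.8%) and zero or negative in 3.

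**2. Nested models, independent units.** One noise term, nominal 5%, 3,000 runs: 6.9% (36 lesions, 12 high grade), 6.7% (50, 15), 6.7% (50, 17), 6.0% (72, 24). In the setting with several lesions per man but no within-man correlation: 5.0–6.1%. This is near nominal.

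**3. Non-nested models, if compared.** FROC has 3 parameters; SEM and kurtosis have 2 each. SEM versus kurtosis gives 2 − 2 = 0 degrees of freedom, so there is no chi-square reference. For 3 versus 2 terms with equal true AUC of 0.75, the share of trials with LR > 3.84 was:

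| Setting | Corr. 0.5 | 0.7 | 0.9 |
|---|---|---|---|
| 50 lesions, 15 high grade | 32.3% | 29.5% | 21.4% |
| 72 lesions, 24 high grade | 35.8% | 30.1% | 22.0% |

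With 1–3 lesions per man the range is 22.1–39.3%. The statistic is negative in 38–46% of trials.

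**4. Clustering.** For 36 men, the ordinary test of one lesion-level noise term (3,000 runs) rejects:

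| Within-man correlation | 0.3 | 0.5 | 0.7 |
|---|---|---|---|
| 2 lesions per man | 5.9% | 7.3% | 9.9% |
| 3 lesions per man | 6.9% | 9.2% | 13.6% |

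A man-level noise term, such as a clinical variable, gives 9–14% at 0.5–0.7. At the same correlations a cluster-robust score test gives 5.2–5.6%, and a Wald test with a t reference 6.1–6.8%.

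**5. Optimism in AUC.** Optimism = apparent AUC − AUC on new data. At 50 lesions, 15 high grade, single-parameter true AUC 0.70, between-parameter correlation 0.7 and no variable selection:

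- 3 terms: 0.754 − 0.689 = 0.065
- 5 terms: 0.785 − 0.673 = 0.112

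Over single-parameter AUCs of 0.65–0.70 and 15–17 high grade, the ranges are 0.06–0.09 and 0.10–0.14. Over 36–72 lesions they widen to 0.04–0.11 and 0.08–0.17.

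**6. Cut-offs.** Youden index J = sensitivity + specificity − 1. At 50 lesions, 15 high grade, AUC 0.70: 0.408 − 0.258 = 0.150. The gap is 0.14–0.16 at 50 lesions and 0.12–0.18 over 36–72. The 90%-sensitivity cut-off has mainly a precision problem: mean true sensitivity is 87–89% at 50 lesions, but an observed 14/15 has an exact 95% interval of 0.68 to 0.998.

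**The case against.** The strongest reply is that *iteratively* most naturally means adding terms to a growing model. On that reading the models are nested, the test is a legitimate test of added value, and only the wording needs correcting. That stands as far as it goes; the text does not commit to it.

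A reader might infer that the plan sets FROC, SEM and kurtosis models against one another and so carries a 21–39% false-positive rate. The documents do not support this. Study Design and Procedures lists the parameters for individual accuracy analysis, and no section states such a comparison. An analyst would also notice a zero-degree-of-freedom or negative statistic.

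A reader might also infer that every secondary analysis is per lesion. Section 12.0 says so for single parameters and gives no unit for the combined models, the only place where the test is used. If those models are per man, the clustering objection to the test disappears; it remains for the single-parameter intervals, where its size was not computed. The effect on the test is also small at the lower end: 6–8% at an assumed correlation of 0.3.

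The optimism figures depend on model size, which the plan does not give. Nothing plans a nine-term model, so figures for models that large are illustrative only. Finally, these are exploratory analyses in a self-declared pilot. That lowers the priority, but it does not make the stated test the right one.

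**Conclusion.** The point holds at moderate priority and for the secondary analyses only; the primary chi-square comparison is untouched.

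Certain from the text: the named test does not test AUC differences; nesting is not required; no clustering method is given; no internal validation is planned.

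Conditional on assumptions:

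- **Nested, independent units:** error near nominal (5–7%), a labelling fault only.
- **Non-nested, 3 versus 2 terms, if compared:** about 21–39%.
- **Several lesions per man as the unit:** roughly 6–14%, by within-man correlation (0.3–0.7) and by whether the added term is lesion-level or man-level. Single-parameter AUC intervals are unreliable to an extent not quantified here.
- **Optimism at 50 lesions, 15–17 high grade:** about 0.06–0.09 in AUC with 3 terms, 0.10–0.14 with 5, and about 0.15 in the Youden index.

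The missing validation is a cheap improvement rather than an error. The documents do not support reading any of these figures as the trial's expected error rate, because they give neither lesion counts nor model sizes.

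**What to change.** Replace the last sentence of Section 12.0 with:

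> The likelihood ratio test will be used only for terms added to a nested model and will be reported as a test of added terms, not of AUC. In any analysis where men contribute several lesions, including single-parameter AUC confidence intervals, methods that allow for clustering by man will be used (clustered DeLong or a bootstrap of men for AUCs; a cluster-robust score test, or a Wald test with a t reference, for added terms). Non-nested models will be compared by the difference in optimism-corrected AUC, with a 95% CI from a bootstrap that resamples men and refits the models; the interval, not a p value, will be the main result. One lesion summary per parameter and a short list of models will be fixed before analysis. Combined-model AUCs and Youden cut-off performance will be reported as apparent and as bootstrap optimism-corrected, with 95% CIs, resampling men and repeating any selection. The 90%-sensitivity cut-offs will be given with confidence intervals.

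The unit of analysis for the combined models should be stated at the same time.

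The correction of the AUC difference matters. A DeLong comparison of apparent AUCs favours the larger model: at 50 lesions, 15 high grade and equal true AUC, 8 versus 2 terms rejects 12% with a spurious gain of 0.07, while 3 versus 2 terms rejects 3–5% with a gain of about 0.015.

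The optimism correction was checked by resampling men (apparent/corrected/true): 0.757/0.698/0.688 with 3 terms and 0.788/0.696/0.673 with 5. For the Youden index with independent lesions, 0.416/0.320/0.261 removes 0.096/0.155 = 62% of the gap, and 0.395/0.297/0.254 removes 0.098/0.141 = 70%. Coverage of the interval for the corrected AUC difference was not simulated.

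Cost: wording and some programming, with no extra patients or procedures. Reported AUCs will be lower, intervals wider and the Youden index only partly corrected. Power is limited: with clustered DeLong on apparent AUCs, a true 0.65 versus 0.80 was detected in 44–68% of trials, which is why the interval should lead. Section 8.0 lists the maximum Gleason score and positive-core location by lesion number, but no explicit grade for each lesion. The planned per-lesion analysis needs that, so it should be confirmed that it can be recovered. Section 13.2 bars analysis until accrual is complete and data are de-identified, so the change can be made before any result is seen.
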